3.1.4. Multiple Assessments

In general, if multiple, valid, non-missing observations exist at a visit or collection time point then records will be chosen based on the following:

- The record closest to the nominal time point in question.

If 2 records are equidistant:

- The later record of the two visits.

If 2 records with same date/time

- Average (generally applies to assessments done in triplicate).

There is a special rule for laboratory test results: if there are multiple valid records within the visit window for the same visit or time point, the record(s) with the latest collection time will be selected rather than the record(s) with collection time closest to the nominal time. The protocol states that:

Additional and repeat laboratory safety testing for the evaluation of abnormal results and/or adverse events during the study may be performed at the discretion of the investigator or upon request of the Sponsor. Repeat laboratory testing of abnormal potentially clinically significant or clinically significant results for Screening evaluation of the subject may be repeated at the discretion of the investigator.

Hence, the latest laboratory test result associated with a visit or time point will be selected for summarization. All results will be provided in listings.

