Clinical laboratory abnormalities of concern may include, but are not limited to, the following where the investigator must recheck within 2-7 days, as deemed appropriate by the investigator, except for AST or ALT > 3x ULN where these need to be rechecked within 48-72 hours:

- clinically significant reduction in leukocytes or leukocyte subsets that may place subjects at higher risk for infection such as:
 - moderate neutropenia (e.g., absolute neutrophil count of < 1.0 x 10⁹/L)

- moderate leukopenia (e.g., white blood cell count of $< 2.0 \times 10^9/L$)
- moderate lymphocytopenia (e.g., absolute lymphocyte count of $< 0.5 \times 10^9/L$)
- abnormal hepatic panel (AST or ALT) $> 3x$ ULN
- an excessive decrease in creatinine clearance (e.g., a reduction by $\geq 50\%$ from baseline, baseline for this purpose is defined as creatinine clearance calculated for Day 1, pre-dose)

Depending on the subject's baseline and individual scenario, the investigator should report as an AESI, and stop study drug treatment if any of the below is seen:

- moderate neutropenia (e.g., absolute neutrophil count of $< 1.0 \times 10^9/L$) on two sequential lab results
- moderate leukopenia (e.g., white blood cell count of $< 2.0 \times 10^9/L$) on two sequential lab results
- moderate lymphocytopenia (e.g., absolute lymphocyte count of $< 0.5 \times 10^9/L$) on two sequential lab results
- a reduction by $\geq 50\%$ from baseline in creatinine clearance on two sequential lab results
- Abnormal AST or ALT $> 3x$ ULN on two sequential lab results with associated bilirubin $> 2x$ ULN on at least one of the two lab results or international normalized ratio (INR) > 1.5 on at least one of the two reports (INR will need to be checked locally),
- ALT or AST $> 8x$ ULN **on a single lab result**
- AST or ALT $> 5x$ ULN on two sequential lab results at least 2 weeks apart, or
- AST or ALT $> 3x$ ULN **on a single lab result associated with signs or symptoms suggestive of acute liver injury** (e.g., the appearance of fatigue, nausea, vomiting, right upper quadrant pain or tenderness, fever, rash, and/or eosinophilia ($> 5\%$)).

[Appendix 12](#) presents an algorithm for evaluating and managing subjects with ALT or AST $> 3x$ ULN

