The first occurrence of these laboratory abnormalities may not trigger the definition of an AESI and study drug discontinuation until the second sequential abnormality (except for the two bolded circumstances above). If there are any questions as to whether a laboratory abnormality should be reported as an AE or an AESI, the investigator is encouraged to contact the Medical Monitor to discuss.

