8.8. Safety Analyses

Safety data will be summarized by treatment received; specifically, induction safety data will be summarized by treatment received during induction and ATE safety data by treatment received during the ATE. Summaries will be provided by nominal visit and time point or for the entire treatment period, as appropriate for the type of data. Quantitative data collected at unscheduled times will be listed but will not be included in summaries. Categorical data collected at unscheduled times (e.g., ECG finding categories) will not be included in summaries by time point but will be included in summaries of findings during the entire treatment period.

[REDACTED]

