3. STATISTICAL ANALYSES

3.1. General Considerations

All data from scheduled and unscheduled visits will be presented in the subject listings.

However, unless noted otherwise, only data from scheduled/windowed visits will be included in the summaries, statistical analysis, and calculation of derived parameters.

Summary tables and listings (e.g., post text tables and individual subject data listings are prepared according to ICH Guideline E3) include a “footer” providing explanatory notes.

Continuous variables will be summarized using an 8-point descriptive summary (number of subjects [n], mean, standard deviation [SD], median [Q2], interquartile range [25th percentile Q1, 75th percentile Q3], minimum, and maximum) unless otherwise indicated. Categorical variables will be summarized by frequency and percentage of subjects in each category. All summaries will be presented by treatment and visit when applicable.

For binary endpoint comparisons to placebo when the expected number of responders/non-responders are less than 5 per treatment groups being analyzed a fishers exact test will be performed. For safety assessments, summary statistics will be reported by treatment.

Analyses and tabulations will generally be prepared using SAS®, version 9.4 or later.

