3.1.3. Visit Windows

All assessments will be summarized using analysis windows.

The terminology of unscheduled will be applied to assessments that are outside an analysis window regardless of the nominal label associated with the assessments in the EDC system.

The following visit windows will be used in the summary of clinical data.

Table 6: Visit Analysis Windows

Nominal Visit	Nominal Day	Start (days)	Stop (days)
Screening	NA	-28	-1
Baseline	1	1	Induction Day 1
Week 4	Induction Day 28	Induction Day 21	Induction Day 35
Week 8	Induction Day 56	Induction Day 49	Induction Day 63
Week 12	Induction Day 84	Induction Day 77	Earliest of: 
 • ATE Day 1 dose date • Induction Day 98 (Induction Day 112 for SES-CD score)
ATE Week 4	ATE Day 28	ATE Day 21	ATE Day 35
ATE Week 8	ATE Day 56	ATE Day 49	ATE Day 63
ATE Week 16	ATE Day 112	ATE Day 105	ATE Day 126
ATE Week 24	ATE Day 168	ATE Day 161	ATE Day 182
ATE Week 36	ATE Day 252	ATE Day 245	ATE Day 266
ATE Week 48	ATE Day 336	ATE Day 329	ATE Day 350

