3.7.3. Additional Safety Assessments

3.7.3.1. Clinical Laboratory Parameters

Laboratory data, hematology, serum chemistry and urinalysis, will be summarized in terms of observed values and changes from baseline for Induction period and overall separately. In addition, changes from baseline relative to normal ranges from the central lab (e.g., shifts from normal to abnormal high/low) will be summarized.

Summaries for laboratory parameters of special interest will also be presented, these will include:

- Neutrophils
- Leukocytes
- Lymphocytes
- Hemoglobin
- Lipids [LDL cholesterol, HDL cholesterol, Cholesterol, and Triglyceride]
- Liver Function Test's [ALT, AST, Bilirubin]
- Creatinine
- Creatinine Kinase

A summary of maximum National Cancer Institute Common Terminology Criteria for Adverse Events (NCI-CTCAE) toxicity grade (Appendix 5.8) for postbaseline laboratory values through Week 12 and ATE Week 48.

Listings will flag laboratory values that are outside of normal range.

A listing of all abnormal lab values will be provided. Listings of subjects with any abnormal postbaseline laboratory values of CTCAE grade ≥ 2 will also be provided.

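### The SAP's latest-record rule for laboratory results has no stated exception for the maximum CTCAE grade table, so an improved in-window recheck can replace a valid worse value and the table can understate transient toxicity.

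*SAP*

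**What the plan says.** Four SAP provisions bear on the table:

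- **Record selection (SAP 3.1.4).** Most assessments use the record closest to the nominal time point. Laboratory results have a special rule that applies when one window holds several valid records: "the record(s) with the latest collection time will be selected rather than the record(s) with collection time closest to the nominal time". It concludes that the latest result for a visit or time point is the one summarized, and that all results are listed.
- **Data used in summaries (SAP 3.1).** Unless noted otherwise, "only data from scheduled/windowed visits will be included in the summaries, statistical analysis, and calculation of derived parameters".
- **Meaning of unscheduled (SAP 3.1.3).** "The terminology of unscheduled will be applied to assessments that are outside an analysis window", whatever the visit label in the data capture system.
- **The table (SAP 3.7.3.1).** It summarizes the maximum "toxicity grade (Appendix 5.8) for postbaseline laboratory values through Week 12 and ATE Week 48". The source records are not named and no exception is noted. The same section adds a listing: "Listings of subjects with any abnormal postbaseline laboratory values of CTCAE grade" 2 or above.

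The protocol supplies the rechecks. Under Protocol 7.2, for neutrophils below 1.0, leukocytes below 2.0 or lymphocytes below 0.5 (all x10^9/L), "the investigator must recheck within 2-7 days". AST or ALT above 3x ULN is rechecked within 48-72 hours. The section adds that a first occurrence "may not trigger the definition of an AESI and study drug discontinuation until the second sequential abnormality", apart from two single-result AST/ALT rules.

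**The concern.** A table of maximum grades is meant to show the worst laboratory value each subject reached. Here the abnormal values of most interest are the ones the protocol requires to be repeated within days, and the SAP then prefers the repeat. The replaced value is a valid result, because the rule applies to multiple valid records and is not limited to faulty samples.

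Safety and tolerability is a primary objective, and Protocol 1.4 names reduced white-cell counts and altered liver tests among the effects seen with a systemic drug of the same class. A transient Grade 3 cytopenia that improves on recheck could appear in a listing and yet be absent from the by-arm grade counts. The AESI summary need not pick it up, since most of the laboratory AESI criteria require two sequential abnormal results.

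For adverse events, by contrast, SAP 3.7.2 does write a worst-case rule: the most severe occurrence per preferred term is counted. Laboratory grades have no equivalent rule.

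**Working it through.** The plan states no figure to reproduce on this point. The check has four steps.

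**1. Direction.** Let A be a subject's valid post-baseline results in the period and S the subset kept by the latest-record rule. Since S is contained in A, max grade(S) <= max grade(A). The table can be too low but never too high.

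**2. Which grades trigger a recheck.** Protocol 7.2 thresholds set against the SAP 5.8 cut-points:

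| Test | Recheck threshold | SAP 5.8 grade | Recheck timing |
|---|---|---|---|
| Neutrophils | <1.0 | 3 or worse | 2-7 days |
| Leukocytes | <2.0 | 3 or worse | 2-7 days |
| Lymphocytes | <0.5 | 3 or worse | 2-7 days |
| AST/ALT | >3x ULN | 2 or worse, if baseline was normal | 48-72 hours |

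**3. How often the recheck shares the window.** Inputs: permitted visit days are nominal -3 to +5 (Protocol 6), which is 9 values. Recheck offsets are 2 to 7 days (6 values, 54 pairs) or 2 to 3 days (2 values, 18 pairs). The Week 4 window is Days 21-35 and the Week 8 window is Days 49-63 (SAP 3.1.3). A pair counts if visit day + offset is no later than Day 35 (or 63). Equal weights are an assumption.

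The SAP window table puts Week 4 at Day 28. SAP 3.1.2 counts the first dose day as Day 1, so four full weeks later is Day 29. Both were counted; Week 8 gives the same results.

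- Nominal Day 28, 2-7 days: visits on Days 25-28 keep all 6 offsets (24). Days 29-33 keep 5, 4, 3, 2 and 1 (15). Total 39/54 = 72.2%.
- Nominal Day 29, 2-7 days: Days 26-28 keep all 6 (18). Days 29-34 keep 5, 4, 3, 2, 1 and 0 (15). Total 33/54 = 61.1%.
- Nominal Day 28, AST/ALT: Days 25-32 keep both offsets (16) and Day 33 keeps 1. Total 17/18 = 94.4%.
- Nominal Day 29, AST/ALT: Days 26-32 keep both (14), Day 33 keeps 1 and Day 34 keeps 0. Total 15/18 = 83.3%.
- Visit exactly on its nominal day: 6/6 (Day 28) or 5/6 (Day 29) for 2-7 days, and 2/2 for AST/ALT.

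The remaining 15 to 21 of the 54 pairs fall on Days 36-41 (Days 64-69 for Week 8), before the next window opens on Day 49 (Day 77). In those cases the first value stays selected.

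Other visits differ. At Week 12, for subjects entering the extension, the window closes at the ATE Day 1 dose date. With visits on Days 84-87, ATE Day 1 falling 1-7 days later, and rechecks counted up to and including that date, the overlap is 84/168 (50%) and 44/56 (79%). From ATE Week 16 the windows run to nominal +14 days, while the latest permitted recheck is at +5 + 7 = +12 days, so all pairs overlap (54/54 and 18/18).

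**4. What is tabulated.**

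- Neutrophils 0.9 on Day 28, then 1.2 on Day 32: 0.9 is Grade 3 (0.5 to <1.0) and 1.2 is Grade 2 (1.0 to <1.5). All valid records give Grade 3; the latest record gives Grade 2. The two-result AESI criterion is not met.
- ALT 3.6x then 2.7x ULN, normal baseline: Grade 2 from all records, Grade 1 from the latest.

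One lost subject is 1/60 = 1.7 or 1/40 = 2.5 percentage points. Event and recovery rates are not in the documents. As an assumed illustration, suppose 4 of 60 subjects in an arm (6.7%) had a Grade 3 value. If 1, 2 or 3 of them were displaced, the table would show 3/60 (5.0%), 2/60 (3.3%) or 1/60 (1.7%).

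**The case against.** The strongest reply is that the latest-record rule is tied to a visit or time point, whereas the maximum-grade table spans a whole period, so a rule for choosing one record per visit need not govern it. The displaced value also comes from a scheduled visit inside its window, so SAP 3.1 does not itself exclude it. A programmer could therefore reasonably take the maximum over every post-baseline value. That reading is open, but the SAP does not state it. SAP 3.1.3 puts all assessments through analysis windows, SAP 3.1.4 selects one record per window for summarization, and nothing exempts this table.

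Protocol 8.8 may also be cited: categorical data from unscheduled times "will be included in summaries of findings during the entire treatment period". This suggests that whole-period displays were meant to be inclusive. However, its example is ECG categories, and the preceding sentence keeps unscheduled quantitative data out of summaries. Under the SAP's own definition, the displaced first value is not unscheduled at all.

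The remaining mitigation is real but partial. All results are listed, and Grade 2 or worse values have their own listing. A clinically significant abnormality may be recorded as an adverse event and tabulated by arm, but that depends on investigator judgement. A worse value in another window still counts. None of this restores the by-arm grade counts.

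It is also fair to say that the overlap percentages measure a precondition. They do not estimate how many grades are lost.

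**Conclusion.** The concern holds. Followed as written, the SAP's record rules allow a valid worse laboratory value to be replaced by an improved recheck in the maximum CTCAE grade table, and the error can run only towards lower grades. The required recheck timing makes the overlap common at Weeks 4 and 8 (61-72%, and 83-94% for AST/ALT) and certain from ATE Week 16.

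How often a grade would be lost is unknown. It also requires the recheck to improve by at least one grade and no other selected visit to be as high. The percentages rest on equally weighted days. The 1.7 and 2.5 point figures rest on the planned arm sizes; the SAP excludes two sites from every analysis set, so actual denominators may differ. The AST/ALT grades assume a normal baseline.

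This should be fixed because it affects the by-arm worst-grade display for a primary safety objective. It does not touch the primary efficacy analysis, and no data are lost. If the inclusive reading was always intended, the change simply records it.

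**What to change.** - In SAP 3.1.4, limit the latest-record rule to by-visit descriptive laboratory summaries.
- In SAP 3.7.3.1, state that the maximum CTCAE grade is the worst grade among all valid post-baseline results in the period, from scheduled, repeat and unscheduled samples. Naming unscheduled samples also covers values that fall between windows (for example Days 36-48), which SAP 3.1 would otherwise leave out.
- As a separate point, apply the same record rule to the counts required by Protocol 8.8.4 that the grade table does not supply, mainly a fall of 50% or more in creatinine clearance and ALT/AST above 8x ULN.

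The cost is one or two SAP sentences and a small programming change. No new data are needed, and no recheck or stopping rule changes.

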3.1.5. Study Period Definitions

3.1.5.1. Induction Period

For analysis and summaries of the induction period, only data collected for each subject from first dose up until the earliest event between the ATE Day 1 dose or date of last dose + 5 days will be presented.

3.1.5.2. Active Treatment Extension Period

Active Treatment Extension is the period from first dose at ATE Day 1 until date of last dose + 5 days.

3.1.5.3. Overall Study Period

For analysis and summaries of the overall study period, only data collected for each subject from first dose up until date of last dose + 5 days will be presented.

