6.3.14. End of Study

An EOS visit will be required for all subjects 4 weeks following their last dose of study drug. Subjects who complete an Early Study Drug Discontinuation visit during Induction or ATE will also be required to return for an EOS visit.

Subjects should be instructed to fast from food and non-clear fluids on the evening prior to the EOS visit to ensure a minimum 8-hour fast prior to the fasted blood sample collection.

The following procedures will be performed at the EOS visit:

- Vital signs
 - Heart rate (HR) and systolic and diastolic blood pressure (BP)
 - Respiratory rate
 - Body Temperature
- 12-lead ECG
- Physical examination is to be conducted according to local practice
- Fistula drainage assessment (if applicable) to determine the number of fistula and confirm draining is occurring.
- Weight
- Blood collection
 - Hematology
 - Serum chemistry
 - Overnight fasting lipid panel
 - [REDACTED]
 - [REDACTED]
- Urine collections
 - Urinalysis
 - Pregnancy test for females of childbearing potential – If urine b-hCG test is positive, confirmation with serum b-hCG test is required

- Disease Assessments
 - CDAI Components
 - Abdominal Pain and Total Stool Frequency Scores
- Review concomitant medications
- Adverse event assessment (AEs, SAEs, Adverse Events of Special Interest)
- Review diary completion and compliance and collect diary from subject

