3.7.2. Adverse Events

Adverse events (AEs) will be coded to the preferred terms (PT) of the Medical Dictionary for Regulatory Activities (MedDRA®). Summaries for induction period and for the complete study period will be presented separately and by system organ class (SOC), preferred term, and severity and/or relatedness, the number and percentage of subjects for whom events were reported.

Adverse events (AEs) are recorded from signing of the informed consent form through the final follow-up assessment. Adverse events observed prior to first dose are non-treatment emergent.

All summaries will be presented for both the Induction Period and the overall study period separately.

Treatment emergent adverse events are defined as follows for induction period and overall:

- Induction period TEAEs are events with a start date/time after the first dose date/time in Induction period up to the date/time of ATE Day 1 dose or date of last dose of study drug + 28 days, whichever is earlier.
- TEAEs for the whole study and listings are defined as AEs with onset on or after the first initiation of study drug up to the date of last dose study drug + 28 days.

Only treatment-emergent AEs will be summarized in the tables. Separate by-subject listings of all TEAEs and all non-TEAEs will be provided.

An AE will be considered a treatment-emergent serious AE (TESAE) if it is a TEAE that additionally meets any SAE criteria.

If more than 1 AE is coded to the same preferred term for the same subject, the subject will be counted only once for that preferred term using the most severe and most related occurrence for the summarizations by severity and by relationship to study drug.

Summary tables will also be provided for Induction period and overall for subjects with:

- TESAEs by SOC and PT
- TEAEs leading to discontinuation of study drug by SOC and PT
- Drug related TEAEs by SOC and PT
- TEAEs by severity and by SOC and PT
- TEAEs resulting in death by PT

Listings of all AEs, SAEs, and AEs leading to premature study drug discontinuation by subject will be presented.

An overall summary of adverse events will also be presented and will include the following summary lines: Any AE, Moderate or Severe AEs, AEs Related to Study Drug, Moderate or Severe AEs Related to Study Drug, Serious AEs, Serious AEs Related to Study Drug, AEs Leading to Premature Study Drug Discontinuation, AEs Leading to Temporary Interruption of Study Drug, and Deaths During Study.

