3.7.3.2. Vital Signs

Descriptive statistics for vital signs (systolic and diastolic blood pressures, pulse rate, and weight) and changes from baseline values at each visit and at the end of study will be presented by treatment group.

For each nominal time point, vital signs will be summarized in terms of observed values and changes from baseline. Marked abnormalities as defined in Table 8 will be flagged in the listing.

Table 8: Criteria for Marked Abnormalities in Vital Signs

Heart Rate (bpm)	Systolic Blood Pressure (mm Hg)	Diastolic Blood Pressure (mm Hg)
< 40	< 85	< 45
> 110	> 160	> 100

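### The SAP's period and window rules keep End of Study laboratory values out of every by-visit and maximum-grade summary, and contradict its end-of-study vital-sign and ECG summaries

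*SAP*

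**What the plan says.** **Study periods (SAP 3.1.5).** All three definitions stop at or before 5 days after the last dose.
- Induction (3.1.5.1) runs from first dose to "the earliest event between the ATE Day 1 dose or date of last dose + 5 days will be presented".
- ATE (3.1.5.2): "Active Treatment Extension is the period from first dose at ATE Day 1 until date of last dose + 5 days".
- Overall (3.1.5.3): "only data collected for each subject from first dose up until date of last dose + 5 days will be presented".

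**Windows (SAP 3.1 and 3.1.3).** All assessments are summarized by analysis window. Table 6 ends with ATE Week 48 (ATE Day 350) and has no EOS or follow-up row. "The terminology of unscheduled will be applied to assessments that are outside an analysis window regardless of the nominal label". Under SAP 3.1, data outside the windows are listed but not summarized, unless the SAP notes otherwise.

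**What is collected (Protocol 6.3.14).** "An EOS visit will be required for all subjects 4 weeks following their last dose of study drug". The visit includes hematology, chemistry, fasting lipids, urinalysis, 12-lead ECG and vital signs. Protocol Section 6 allows it from 3 days early to 5 days late.

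**What the safety sections promise.**
- Laboratory (SAP 3.7.3.1): summaries for Induction and overall, and a maximum-grade table for "postbaseline laboratory values through Week 12 and ATE Week 48". End of study is not mentioned.
- Vital signs (SAP 3.7.3.2): "changes from baseline values at each visit and at the end of study will be presented by treatment group".
- ECG (SAP 3.7.3.3): statistics at each time point through the end of study.
- Whole-study treatment-emergent adverse events (SAP 3.7.2): "up to the date of last dose study drug + 28 days". SAP 3.2.5 uses the same 28 days for concomitant medications.

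**The concern.** Safety and tolerability is a primary objective. Protocol 1.4 names cell-count falls, liver tests, creatinine and lipids among the effects seen with a systemic JAK inhibitor, and relies on laboratory monitoring to watch for them. The EOS panel is the scheduled assessment that shows whether such changes persist, worsen or recover after drug is stopped. If it reaches no summary table, the report cannot describe reversibility by arm even though the data exist.

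The exclusion does not look deliberate. The vital-sign and ECG sections expect end-of-study results, and the adverse-event section follows subjects for 28 days. The general rules in 3.1.3 and 3.1.5 appear not to have been checked against them.

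**Working it through.** **1. The protocol's own duration.** Screening 5 + Induction 12 + ATE 48 + follow-up 4 = 69 weeks, as the synopsis states. The 4-week follow-up is a planned part of participation.

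**2. EOS timing against the cut.**
- Earliest on-time EOS: 28 − 3 = day 25 after last dose. Latest: 28 + 5 = day 33.
- Distance beyond the 5-day limit: 25 − 5 = 20 days to 33 − 5 = 28 days.
- No on-time EOS visit can fall inside any of the three periods.

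The protocol gives two anchors for this visit. The End of Study paragraph of Section 3.1 and Section 6.3.14 count 4 weeks from the last dose. The Early Study Drug Discontinuation paragraph of Section 3.1 counts 4 weeks from the discontinuation visit, which is itself up to 5 days after the last dose. On the second reading the latest on-time visit is 5 + 28 + 5 = day 38. The conclusion is the same either way.

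**3. EOS against Table 6, ATE completers.** Last dose at ATE Week 48 falls on ATE Day 336 − 3 = 333 to 336 + 5 = 341. EOS is then Day 333 + 25 = 358 to 341 + 33 = 374. The last window closes at Day 350, so both the window rule and the period rule exclude it.

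**4. EOS against Table 6, early stoppers.** With nominal EOS at last dose + 28, I counted the last-dose days that put EOS inside a Table 6 window.
- Induction, last dose Day 1 to 83: Week 4 window 7 days, Week 8 window 15, Week 12 window 22. Total 44 of 83.
- ATE, last dose ATE Day 1 to 335: 7 + 15 + 4 × 22 = 110 of 335.

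In these cases only the 5-day cut removes the value. For example, a last dose on Day 30 gives EOS on Day 58, inside the Week 8 window (Day 49 to 63). SAP 3.1.4 takes the latest laboratory record in a window, so lifting the cut without adding an EOS row could report an off-drug value as Week 8.

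**5. Effect by data type.**

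| Data | End-of-study wording in its own section? | Result |
|---|---|---|
| Laboratory | No; grade table stops at ATE Week 48 | EOS values listed only |
| Vital signs | Yes (3.7.3.2) | Contradiction with 3.1.3 and 3.1.5 |
| ECG | Yes (3.7.3.3) | Contradiction with 3.1.3 and 3.1.5 |
| Adverse events, concomitant medications | Own 28-day rules | Not affected |

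**6. Would a 28-day cut be enough?** The permitted EOS days are 25 to 33, nine days in all. A cut at day 28 keeps days 25 to 28 and loses days 29 to 33, which is 5 of the 9.

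**The case against.** The strongest defence is that little of clinical importance is lost. Much of it stands.

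- **Adverse events cover the serious cases.** Laboratory abnormalities of concern are an AESI category (Protocol 7.1.4, SAP 3.7.2.1), and other clinically significant findings may be recorded as adverse events. A reader might infer that laboratory toxicity is followed for only 5 days and clinical toxicity for 28. The documents do not support that: a delayed fall in counts or a liver-test peak can reach the adverse-event tables. These tables do not carry the values themselves, sub-threshold shifts (including lipids) or recovery.
- **Listings remain.** All data are listed, with listings of abnormal values and of subjects with grade 2 or higher. Listings do not compare arms.
- **Vital signs and ECG may be exceptions.** SAP 3.1 allows for text that notes otherwise, and 3.7.3.2 and 3.7.3.3 may be that text. So for these two the defect is an unresolved contradiction, not a settled omission. No window or period rule says how to carry the exception out.
- **EOS is not the only off-drug assessment.** The Early Study Drug Discontinuation visit, within 5 days of last dose where possible, includes laboratory tests and ECG. EOS is the later assessment, about 4 weeks off drug.
- **Few subjects have a placebo comparison.** Subjects who complete Induction go on to TD-1473 in ATE, with placebo subjects moving to 80 mg. A concurrent placebo comparison at EOS exists only for those who stop during Induction, a self-selected group.

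A reader might also infer that the cut removes the rechecks in Protocol 7.2. That does not follow. Most of the stopping criteria need two sequential results, so the recheck normally comes before stopping. The single-result triggers concern AST or ALT above 3 times the upper limit, where the recheck is due within 48 to 72 hours, normally inside 5 days.

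**Conclusion.** The point holds for laboratory data. Read as written, the SAP keeps every on-time EOS hematology, chemistry, lipid and urinalysis value out of its by-visit and maximum-grade summaries. For vital signs and ECG, the general rules and the safety sections contradict each other and must be reconciled.

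The gap is 20 to 28 days beyond the cut, so no on-time visit escapes it. This rests on the protocol's visit tolerance and on applying SAP 3.1.5 to laboratory summaries, which the laboratory section does not override.

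The number of panels affected cannot be fixed from the documents. It is at most one per dosed subject against 160 planned. The SAP records early termination and removes two sites from all analysis sets, and some subjects will not attend.

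A reader might go further and conclude that all safety follow-up beyond 5 days is discarded, or that every EOS visit lies outside both the periods and the windows. Neither is supported, given the 28-day rules and the 44 of 83 and 110 of 335 counts above. The loss is the by-arm description of off-drug values and recovery. It bears on a primary objective and should be corrected.

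**What to change.** 1. **SAP 3.1.5.** State that the 5-day limit does not apply to laboratory, ECG and vital-sign safety summaries.
2. **SAP Table 6.** Add a separate EOS / post-treatment time point anchored to the last dose of study drug. It covers more than 5 days after that dose through the EOS visit, for subjects who are not continuing into ATE.
3. **Precedence rule (SAP 3.1.4).** Any value more than 5 days after the last dose goes only to this time point, never to an on-treatment window such as Week 8 or Week 12.
4. **SAP 3.7.3.1 to 3.7.3.3.** Summarize EOS values and changes from baseline by arm, apart from on-treatment visits, with a separate post-treatment maximum CTCAE grade. Align the end-of-study wording in the vital-sign and ECG sections with the new time point.
5. **Upper window limit.** Set it after the protocol's two EOS anchors (4 weeks after last dose, and 4 weeks after the Early Study Drug Discontinuation visit) have been reconciled. A limit of last dose + 28 days would be too short under either.

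The cost is SAP wording and a little more table work, with no new data. The downside is that off-drug values must be shown separately, and text beside the tables should say that only subjects who stopped in Induction give a concurrent placebo comparison.
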